3.1 Administration Schedule

JNJ-42756493 (erdafitinib) is administered orally at least 1 hour before eating or at least 2 hours after a meal at the prescribed dose (flat dose) daily continuously, for 28 days of every 28-day cycle.

At start, JNJ-42756493 (erdafitinib) is administered orally at the dose of 8 mg throughout the first 14 days of a 28-day cycle.

[figure not shown]
Rev. Add16

Dose Up-titration Guidelines

For subjects, treatment will be up-titrated or maintained based on phosphate level measured on Cycle 1 Day 15, and taking into account observed toxicity to that day, as described in Figure 1. The up-titrated dose would be given starting on Cycle 1 Day 15, for the remainder of the treatment.

Further treatment modification or termination will be based on toxicity as described below. For eye, skin/nail, dry mouth/mucositis, liver, and phosphate toxicity, specific recommendations in the management guidelines are provided below.

Figure 1: Dose Up-titration

* PO4 assessments are done as per T&E; dose up-titration decision is based on C1D15 assessment and up-titrated dose to be administered starting C1D15.

** Drug related toxicity during Cycle 1 as determined by investigator. At any time during treatment with study drug, dose interruptions/modifications would be managed by investigator as clinically indicated. Specific recommendations on dose reductions and toxicity management are provided throughout Section 3.4.

Tablets should be taken with 8 ounces of water and swallowed intact. Each dose should be taken at least 1 hour before eating or at least 2 hours after a meal, at approximately the same time each day. Subjects should avoid consuming grapefruit or Seville oranges while on study treatment due to CYP450 3A4/5 inhibition.

JNJ-42756493 (erdafitinib) should be administered daily at approximately the same time, and the interval between two consecutive doses should be approximately 24 hours. Missed doses for any reason (including vomiting following drug administration) can be taken up to 6 hours after the scheduled time. If it has been more than 6 hours since the missed dose, then that dose should be skipped.

Repeat cycles until progression.

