1.2 Supporting Preliminary Data

1.2.1 First-In-Human Study

Janssen conducted a phase 1 FIH study in patients with advanced cancer, including a subgroup of patients demonstrating FGFR aberrations, with several expansion cohorts and 2 schedules (daily and a 7 day on, 7 day off schedule).¹ The recommended dose on the daily schedule was 9 mg; recommended dose on the intermittent schedule was 10 mg. AUC was dose-proportional and apparent T1/2 was fairly long (50-60h). Among 23 response-evaluable patients with tumor FGFR pathway alterations, four confirmed partial responses and one unconfirmed partial response were seen in patients with glioblastoma and urothelial and endometrial cancer, all with FGFR2 and FGFR3 translocations. Median duration of response was 7.2 months and median PFS was 5.1 months. Common adverse events include hyperphosphatemia (manageable with treatment interruption), dry skin and nail toxicities. Drug-related gr ≥ 3 AEs were onycholysis, paronychia, and hand-foot syndrome. DLT: 1 at 12 mg (Gr 3 LFT elevation).

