In this study (Study EDI1001), 125 subjects (98%) experienced a TEAE; 68 subjects (54%) experienced a Grade 3 or higher TEAE. The 5 most common adverse events (35% or greater) in the total population are hyperphosphatemia, dry mouth, asthenia, constipation, and stomatitis. Other commonly observed effects include skin and nail changes, which are considered adverse drug reactions. Grade 3 or higher TEAEs were reported for 65 subjects (51%). The most common were elevated aspartate aminotransferase and hyponatremia, reported for 7 subjects each. Ten (10) subjects (8%) had treatment-emergent adverse events that resulted in discontinuation of treatment. General physical health deterioration was the only event that led to discontinuation by more than 1 subject. Adverse events of special interest include events that are class effects of FGFR inhibitors and have been experienced by patients treated with other FGFR inhibitors. These events include skin, mucosal, and nail changes and hyperphosphatemia, fatigue, and reversible retinal pigment epithelial detachment (RPED or central serous retinopathy[CSR]). Fifty subjects (39%) were reported with serious adverse events. The most frequently reported serious events (by 5 or more subjects) were general health deterioration, dyspnea, and intestinal obstruction. A total of 16 subjects have discontinued from Study EDI1001 due to death. Of these, 13 deaths were within 30 days of last dose. The primary cause of most deaths within 30 days was progressive disease (9/13 subjects). For 3 subjects, the primary cause of death was an adverse event. These were not drug related, and were anemia and sepsis in 1 subject, pulmonary edema in 1 subject, and cerebral hemorrhage in 1 subject.

In patients, JNJ-42756493 exhibited dose-related increase in Cmax and AUC and time-independent PK within the dose range of 0.5 mg to 12 mg, both after single and multiple daily dosing. Median Tmax observed ranged from 2 to 4 hrs (JNJ-42756493 as capsule). JNJ-42756493 is highly bound to plasma proteins such as α 1-Acid

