Glycoprotein (α 1-AGP). In patients, free fractions of JNJ-42756493 in human plasma were small (average~0.36%). JNJ-42756493 is a P-glycoprotein (P-gp) substrate. In vitro data suggested the metabolism of JNJ-42756493 was limited, leading to a low amount of metabolites being formed. CYP3A4 is the dominant CYP450 enzyme involved. Long terminal phase halflife of JNJ-42756493 (>50 hrs) in plasma was observed resulting in approximately 3-fold accumulation of Cmax and AUC following multiple daily dosing.

A poster at ESMO2016 presented data in urothelial carcinoma (UC) patients from the same Phase 1 study. Thirty pts with UC were treated at 2 mg QD (n=1), 9 mg QD (n=12), 10 mg ID (n=15), 12 mg QD (n=1), or 12 mg ID (n=1). Across these dose levels, median treatment duration was 3.3 months (mo). The most common drug-related AEs were hyperphosphatemia (53%), dry mouth (47%), diarrhea (43%), and dry skin (43%); all of these were grade 1 or 2 severity, except for 1 case of grade 3 hyperphosphatemia (3%) and 2 cases of grade 3 diarrhea (7%). The most common grade \geq 3 AEs were anemia (17%), hand-foot syndrome (13%), and stomatitis (11%). Among FGFR-mutated or translocated, response evaluable UC pts (as of 06 Jun 2016), 7/11(63.6%) pts were treated at 9 mg QD and achieved PR with median duration of response of 7.2 mo (95% CI 3.8, 15.3), and 4/13 (30.8%) pts were treated at 10 mg ID and achieved PR.

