5.1.5 Dose Specifics

JNJ-42756493 (erdafitinib) tablets will be administered orally once a day on a continuous daily dosing schedule on a 28-day cycle. Dose reductions are allowed according to Section 3.4.

JNJ-42756493 (erdafitinib) dose	Use tablet strengths
8 mg	2 x 4 mg
6 mg	2 x 3 mg
9 mg	3 x 3 mg

5.1.6 How Supplied:

Janssen Pharmaceuticals supplies and CTEP, NCI, DCTD distributes JNJ-42756493. The agent is available as 3 mg (yellow), 4 mg (orange), and 5 mg (brown) film coated tablets. The approximate dimensions of the round tablets are in the table below:

Strength	Diameter (mm)	Thickness (width) (mm)
3 mg	7.7 \pm 0.2	3.7 \pm 0.4
4 mg	8.2 \pm 0.2	4.2 \pm 0.4
5 mg	8.7 \pm 0.2	4.6 \pm 0.4

JNJ42756493 tablets are provided in 30 count bottles made of high density polyethylene (HDPE), with an induction seal and child resistant cap. Tablets must be dispensed in the original container.

Tablet excipients include mannitol, microcrystalline cellulose, meglumine, croscarmellose sodium, magnesium stearate, and Opadry AMB II.

5.1.7 Route of Administration:

Oral. Take tablets at least 1 hour before eating or at least 2 hours after a meal at approximately the same time each day. Tablets must be swallowed whole with 8 ounces of water. Do not crush or chew.

If a dose is missed, it can be taken up to 6 hours after the scheduled time; the subject may return to the normal schedule the following day. If it has been more than 6 hours since the missed dose, then that dose should be skipped and the subject should continue treatment at the scheduled time the next day.

5.1.8 Incompatibilities:

JNJ-42756493 shows weak inhibition potential towards CYP1A2, CYP2C9, CYP2C19, CYP2D6, and CYP3A4. No clinical studies have been conducted yet for JNJ-42756493 regarding the potential for drug-drug interactions in humans.

CYP3A4 and CYP2C9 can be considered the dominant CYP450 enzymes involved in the microsomal metabolism of JNJ-42756493. With CYP2D6 and CYP2C8 can potentially be involved to a minor extent. Caution is to be exercised in combining JNJ-42756493 with strong inhibitors/inducers of CYP3A4/5 and CYP2C9. Subjects should be closely monitored for potential toxicities, and appropriate action, including temporary interruption of JNJ-42756493, as appropriate should be taken.

JNJ-42756493 has intermediate to high permeability with some indication of a P-glycoprotein (P-gp) efflux mechanism. Potent inhibitors of P-gp should be contraindicated.

5.1.9 Side Effects:

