Appendix I

Patient Pill Calendar

Storage: Store intact bottles at controlled room temperature 15°C to 30°C (59 to 86°F).

Pill Calendar Directions

1. Take your scheduled dose of each tablet.
2. If you forget, the missed tablets can be taken up to 6 hours after the scheduled time. If it has been more than 6 hours since the missed dose, that dose will be skipped and you will resume treatment at the next scheduled time.
3. Please bring the empty bottle or any leftover tablets and your pill calendar to your next clinic visit.
4. Tablets must be swallowed whole with 8 ounces of water. Do not crush or chew.
5. Tablets should be taken at least 1 hour before eating or 2 hours after a meal, at approximately the same time each day.
6. Subjects should avoid consuming grapefruit or Seville oranges while on study treatment.

Patient Pill Calendar

This is a calendar on which you are to record the time and number of tablets you take each day. You should take your scheduled dose of each tablet. **Note the times and the number of tablets that you take each day.** If you develop any side effects, please record them and anything you would like to tell the doctor in the space provided. Bring any unused tablets and your completed pill calendar to your doctor's visits.

JNJ-42756493 (erdafitinib) dose	Use tablet strengths
3 mg	1 x 3 mg
4 mg	1 x 4 mg
5 mg	1 x 5 mg
6 mg	2 x 3 mg
8 mg	2 x 4 mg
9 mg	3 x 3 mg

JNJ-42756493 (Erdafitinib)

DAY	Date			Time tablets taken	Number of tablets taken			Use the space below to make notes about things you would like to tell the doctor (including unusual symptoms you experience, other medicine you have taken and anything else you think would be of interest.)
	Month	Day	Year		3 mg	4 mg	5 mg	
1								
2								
3								
4								
5								
6								
7								
8								
9								
10								
11								
12								
13								
14								
15								
16								
17								
18								
19								
20								
21								
22								
23								

DAY	Date			Time tablets taken	Number of tablets taken			Use the space below to make notes about things you would like to tell the doctor (including unusual symptoms you experience, other medicine you have taken and anything else you think would be of interest.)
	Month	Day	Year		3 mg	4 mg	5 mg	
24								
25								
26								
27								
28								

Patient Signature: _____ Date: _____

**Molecular Analysis for Therapy Choice (MATCH)
MATCH Treatment Subprotocol K1: JNJ-42756493 (Erdafitinib), FGFR Amplifications**

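### Section 3.1 lets a dose vomited hours after intake be retaken as if missed; after about 3 hours the repeat is probably mostly extra drug (minor)

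*Protocol*

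**What the plan says.** Section 3.1 (Administration Schedule) sets one catch-up rule for every kind of missed dose: "Missed doses for any reason (including vomiting following drug administration) can be taken up to 6 hours after the scheduled time". It then closes the window: "If it has been more than 6 hours since the missed dose, then that dose should be skipped". Both limits run from the scheduled or missed dose. Neither refers to the time between swallowing the tablets and vomiting.

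Two other places repeat the window without mentioning vomiting. Section 5.1.7 says "If a dose is missed, it can be taken up to 6 hours after the scheduled time". The Appendix I pill calendar says "If you forget, the missed tablets can be taken up to 6 hours after the scheduled time". So only Section 3.1 deals with vomiting, and the other two places do not limit it.

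The relevant pharmacokinetics are in Section 1.2.1: "Median Tmax observed ranged from 2 to 4 hrs (JNJ-42756493 as capsule"), "AUC was dose-proportional and apparent T1/2 was fairly long (50-60h"), and a long terminal phase "resulting in approximately 3-fold accumulation of Cmax and AUC following multiple daily dosing". The data there cover once-daily doses "within the dose range of 0.5 mg to 12 mg, both after single and multiple daily dosing".

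**The concern.** A 6-hour catch-up window suits a tablet that was never taken. A dose that was swallowed and later vomited is different, because part or all of it may already be absorbed. Read plainly, Section 3.1 lets a patient who takes the dose on time and vomits at hour 5 take a second full dose before hour 6. If absorption is nearly complete by then, the second dose replaces nothing.

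What is at stake is one unneeded dose, in a patient who is already vomiting, of a drug that takes days to clear. The same section asks for about 24 hours between doses. A repeat at hour 6 puts two doses 6 hours apart and the next one 18 hours later.

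**Working it through.** The protocol gives no figure of its own on this point, so this is a plausibility check on its stated pharmacokinetics.

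**Inputs.** From Section 1.2.1: median Tmax 2-4 h (capsule; this trial uses film-coated tablets), half-life 50-60 h, about 3-fold accumulation. From Section 3.1: daily dose 8 mg, up-titrated to 9 mg.

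**Consistency of the inputs.** With k = ln 2 / half-life, accumulation on 24-h dosing is 1/(1 − e^(−24k)): 3.53 at 50 h and 4.13 at 60 h. Exactly 3-fold needs 24·ln 2/ln 1.5 = 41 h, so 41 h is carried as a sensitivity value.

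**Share absorbed, one compartment.** Solve Tmax = ln(ka/k)/(ka − k) for ka, then absorbed share = 1 − e^(−ka·t).
- Tmax 2 h: ka = 2.64-2.75 per h, more than 99.9% absorbed by 3 h.
- Tmax 4 h: ka = 1.11-1.17 per h, 96-97% by 3 h and about 99% by 4 h.

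**Sensitivity to slower absorption.**
- Two compartments (assumed distribution half-life 2 or 4 h carrying 30-70% of the intercept, terminal 55 h): at Tmax 2 h, about 95% or more by 3 h. At Tmax 4 h, ka = 0.34-0.74 per h, giving 64-89% by 3 h, 75-95% by 4 h and 82-97% by 5 h.
- Zero-order absorption ending at Tmax: 75% by 3 h at Tmax 4 h, otherwise 100%.

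In every case more than half the dose is in by 3 h.

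**Break-even.** When half the dose is absorbed, repeating overshoots by as much as not repeating undershoots. That time is ln 2/ka: 0.25-0.62 h (one compartment) and 0.38-2.04 h (two compartments). It counts all unabsorbed drug as lost, which favours repeating.

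**Size of a full repeat at hour 6, at steady state** (one compartment, superposition):

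| Half-life | AUC that day | Peak that day | Next day's peak |
|---|---|---|---|
| 50 h | +21-22% | +20-21% | +22% |
| 60 h | +18% | +18% | +20% |
| 41 h | +25-26% | +24% | +25% |

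The highest peak is the next day's. Once absorption is over, its rise is close to e^(−18k)·(1 − e^(−24k)):
- 50 h: 0.779 × 0.283 = 0.22
- 60 h: 0.812 × 0.242 = 0.20
- 41 h: 0.738 × 0.333 = 0.25

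A repeat at hour 3 adds somewhat more to that day's AUC, 21-25% (29% at 41 h), before deducting the small unabsorbed share. The excess is about 10-11% at 72 h after the repeat and below 5% after about 5-6 days.

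**Against 12 mg daily**, assuming peak is proportional to dose: 8 × 1.20/12 = 0.80 and 9 × 1.25/12 = 0.94. With the hour-3 figure at 41 h, 9 × 1.29/12 = 0.97. All are below 1.

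**The case against.** **The rule is permissive and can be read narrowly.** It says a dose can be taken, not that it must be. It might cover only doses truly lost, and the notes to Figure 1 leave dose management to the investigator. This stands in part: nothing directs a repeat. But Section 3.1 is the text that site staff apply, and it gives them no ground for declining one.

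**Favouring exposure is a legitimate choice.** Section 1.3 wants as many patients as possible in the phosphate target range, and over equal 24-hour windows one lost dose and one extra dose move AUC by the same 24-28%. That supports replacing a dose that was lost. It does not support repeating one that is already absorbed.

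**The 3-hour mark is soft.** It is inferred from a capsule median, and the two-compartment terms are assumed. In the slowest case 36% is still unabsorbed at 3 h. This stands, and is why the claim is only that the repeat is probably mostly extra.

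**Other text may settle it.** The Appendix III handout and the Master Protocol are not at hand. The fasting rule also narrows when a repeat is practicable.

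Three stronger readings are tempting and fail:
- A reader might take most of the 6-hour window as a period of over-dosing. The window limits when the dose is retaken, not when vomiting happened. A patient who vomits at 15 minutes and retakes at hour 5 makes a true replacement.
- A reader might say patients are told to repeat vomited doses. The calendar speaks only of forgetting.
- A reader might infer a threat to the response results or to the Day 15 titration. Nothing in the protocol shows this, and the frequency of late vomiting is not given.

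**Conclusion.** The point holds as a minor one. Section 3.1 permits a repeat after vomiting at any time within its window, and where vomiting itself comes about 3 h or more after intake, most of that repeat is probably additional drug. The cost is a transient excess in an individual patient: for a repeat at hour 6, about 18-22% more AUC that day and a highest peak about 20-22% up, or about 25% for both at a 41 h half-life. The peak stays below that of 12 mg daily, a dose that the first-in-human study covered. That comparison shows the scale and is not proof of safety, since Section 1.2.1 reports one dose-limiting toxicity at 12 mg.

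The conclusion assumes that tablets absorb about as fast as capsules and that Tmax in a vomiting patient is near the stated median. Confidence is medium, and the change is an inexpensive improvement.

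**What to change.** In Section 3.1, delete the parenthesis on vomiting from the 6-hour rule and add: *If vomiting occurs more than 1 hour after intake, the dose is not replaced and dosing resumes at the next scheduled time.* For clarity, add that a dose vomited within that hour may be retaken under the 6-hour rule. Do not require intact tablets to be seen, since that would block fair replacements after prompt vomiting. The sponsor may choose another cut-off of about 0.5-2 h, in line with the break-even times, or the simpler rule that vomited doses are never replaced. Put the same sentence in Section 5.1.7 and the Appendix I directions, and check that the Appendix III handout agrees.

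The cost is a short text change in three places at the next addendum, with no new procedures. The downside is an occasional partly lost dose. At the slowest assumed absorption, vomiting just after 1 hour could lose about 71% of a dose (e^(−0.34) = 0.71). Under the simpler rule, a dose vomited at once is lost whole: about 24-28% of that day's AUC and a trough about 14% low at 72 h. The protocol already accepts a loss of that size for a dose skipped after 6 hours.

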3.2 Adverse Event Reporting Requirements

The Adverse Event Reporting Requirements for all EAY131 subprotocols are outlined in the MATCH MASTER protocol. Please refer to those guidelines when determining if an event qualifies as a Serious Adverse Event (SAE) and requires expedited reporting via CTEP's Adverse Event Reporting System (CTEP-AERS).

In addition, the following section outlines agent specific requirements and must be followed to ensure all reporting requirements are met.

3.2.1 Additional instructions, requirements and exceptions for protocol EAY131 – Subprotocol K1

Additional Instructions

For instructions on how to specifically report events that result in persistent or significant disability/incapacity, congenital anomaly, or birth defect events via CTEP-AERS, please contact the AEMD Help Desk at [contact] or [contact]. This will need to be discussed on a case-by-case basis.

EAY131 – Subprotocol K1 specific expedited reporting requirements:

- **Pregnancies:** Pregnancies and suspected pregnancies (including a positive or inconclusive pregnancy test, regardless of age or disease state) occurring while the subject is on JNJ-42756493 (erdafitinib), or within 28 days of the subject's last dose of JNJ-42756493 (erdafitinib), are considered immediately reportable events. The pregnancy, suspected pregnancy, or positive/ inconclusive pregnancy test must be reported via CTEP-AERS within 24 hours of the Investigator's knowledge. Please refer to Appendix VIII in MATCH Master Protocol for detailed instructions on how to report the occurrence of a pregnancy as well as the outcome of all pregnancies.
- **Ocular events:** Any grade 3 or higher ocular event of any type occurring must be reported via CTEP-AERs in the timeframe outlined in Section 5.3.6 of the EAY131 MASTER protocol for the specific grade being reported.
- **Liver Events:** Any liver adverse event that meets the criteria listed below, with no other explanation for the abnormality, must be reported via CTEP-AERs in the timeframe outlined in

Section 5.3.6 of the EAY131 MASTER protocol for the specific grade being reported.

- ALT $\geq 3 \times$ ULN and bilirubin $\geq 2 \times$ ULN ($> 35\%$ direct bilirubin) (or ALT $\geq 3 \times$ ULN and international normalized ratio [INR] > 1.5 , if INR measured). Exception to the bilirubin elevation is made if the subject has Gilbert's disease and the elevated bilirubin is predominantly unconjugated.
- ALT $\geq 5 \times$ ULN for 2 weeks or ALT > 8 ULN.
- ALT $\geq 3 \times$ ULN if associated with the appearance or worsening of symptoms of liver injury, hepatitis or hypersensitivity such as fatigue, nausea, vomiting, right upper quadrant pain or tenderness, fever, rash or eosinophilia.
- Persistent elevation of ALT $\geq 3 \times$ ULN for ≥ 4 weeks or if ALT elevation cannot be monitored.
- **Hy's law criteria:** If the following criteria are met, then it must be reported via CTEP-AERs in the timeframe outlined in Section 5.3.6 of the EAY131 MASTER protocol for the specific grade being reported
 - (ALT $\geq 3 \times$ ULN and bilirubin $\geq 2 \times$ ULN ($> 35\%$ direct bilirubin) with no evidence of ALP elevation or ALT $\geq 3 \times$ ULN and INR > 1.5 and no alkaline phosphatase [ALP] elevation).

EAY131 – Subprotocol K1 specific expedited reporting exceptions:

For Subprotocol K1, the adverse events listed below do not require expedited reporting via CTEP-AERS:

- If an AE meets the reporting requirements of the protocol, and it is listed on the SPEER, it should ONLY be reported via CTEP-AERS if the grade being reported exceeds the grade listed in the parentheses next to the event.

3.2.2 Second Primary Cancer Reporting Requirements

All cases of second primary cancers, including acute myeloid leukemia (AML) and myelodysplastic syndrome (MDS), that occur following treatment on NCI-sponsored trials must be reported to ECOG-ACRIN using Medidata Rave

- **A second malignancy is a cancer that is UNRELATED to any prior anti-cancer treatment (including the treatment on this protocol). Second malignancies require ONLY routine reporting as follows:**
 1. Complete a Second Primary Form in Medidata Rave within 14 days.
 2. Upload a copy of the pathology report to ECOG-ACRIN via Medidata Rave confirming the diagnosis.

3. If the patient has been diagnosed with AML/MDS, upload a copy of the cytogenetics report (if available) to ECOG-ACRIN via Medidata Rave.
- **A secondary malignancy is a cancer CAUSED BY any prior anti-cancer treatment (including the treatment on this protocol). Secondary malignancies require both routine and expedited reporting as follows:**
 1. Complete a Second Primary Form in Medidata Rave within 14 days
 2. Report the diagnosis via CTEP-AERS at <http://ctep.cancer.gov>
Report under a.) leukemia secondary to oncology chemotherapy, b.) myelodysplastic syndrome, or c.) treatment related secondary malignancy
 3. Upload a copy of the pathology report to ECOG-ACRIN via Medidata Rave and submit a copy to NCI/CTEP confirming the diagnosis.
 4. If the patient has been diagnosed with AML/MDS, upload a copy of the cytogenetics report (if available) to ECOG-ACRIN via Medidata Rave and submit a copy to NCI/CTEP.

NOTE: The Second Primary Form and the CTEP-AERS report should not be used to report recurrence or development of metastatic disease.

NOTE: If a patient has been enrolled in more than one NCI-sponsored study, the Second Primary Form must be submitted for the most recent trial. ECOG-ACRIN must be provided with a copy of the form and the associated pathology report and cytogenetics report (if available) even if ECOG-ACRIN was not the patient's most recent trial.

NOTE: Once data regarding survival and remission status are no longer required by the protocol, no follow-up data should be submitted via CTEP-AERS or by the Second Primary Form.

Rev. Add16
Rev. Add193.3 Comprehensive Adverse Events and Potential Risks List (CAEPR) for JNJ-42756493 (Erdafitinib, NSC 781558)

The Comprehensive Adverse Events and Potential Risks list (CAEPR) provides a single list of reported and/or potential adverse events (AE) associated with an agent using a uniform presentation of events by body system. In addition to the comprehensive list, a subset, the Specific Protocol Exceptions to Expedited Reporting (SPEER), appears in a separate column and is identified with bold and italicized text. This subset of AEs (SPEER) is a list of events that are protocol specific exceptions to expedited reporting to NCI (except as noted below). Refer to the 'CTEP, NCI Guidelines: Adverse Event Reporting Requirements' http://ctep.cancer.gov/protocolDevelopment/electronic_applications/docs/aeguidelines.pdf for further clarification. Frequency is provided based on 417 patients. Below is the CAEPR for JNJ-42756493 (Erdafitinib).

NOTE: If an AE meets the reporting requirements of the protocol, and it is listed on the SPEER, it should **ONLY** be reported via CTEP-AERS if the grade being reported exceeds the grade listed in the parentheses next to the event.

Version 2.2, January 04, 2019¹

Adverse Events with Possible Relationship to Erdafitinib (JNJ-42756493) (CTCAE 5.0 Term) [n= 417]			Specific Protocol Exceptions to Expedited Reporting (SPEER)
Likely (>20%)	Less Likely (<=20%)	Rare but Serious (<3%)	
BLOOD AND LYMPHATIC SYSTEM DISORDERS			
	Anemia		Anemia (Gr 2)
EYE DISORDERS			
	Dry eye		Dry eye (Gr 2)
	Keratitis		
Eye disorders - Other (central serous retinopathy) ²			
	Eye disorders - Other (eye disorders) ³		
GASTROINTESTINAL DISORDERS			
	Abdominal pain		Abdominal pain (Gr 2)
	Constipation		Constipation (Gr 2)
	Diarrhea		Diarrhea (Gr 2)
Dry mouth			Dry mouth (Gr 2)
Mucositis oral			Mucositis oral (Gr 2)
	Nausea		Nausea (Gr 2)
	Vomiting		Vomiting (Gr 2)
GENERAL DISORDERS AND ADMINISTRATION SITE CONDITIONS			
	Fatigue		Fatigue (Gr 2)
	Fever		Fever (Gr 2)

Adverse Events with Possible Relationship to Erdafitinib (JNJ-42756493) (CTCAE 5.0 Term) [n= 417]			Specific Protocol Exceptions to Expedited Reporting (SPEER)
Likely (>20%)	Less Likely (<=20%)	Rare but Serious (<3%)	
INFECTIONS AND INFESTATIONS			
	Conjunctivitis		
	Paronychia		Paronychia (Gr 2)
INVESTIGATIONS			
	Alanine aminotransferase increased		Alanine aminotransferase increased (Gr 2)
	Aspartate aminotransferase increased		Aspartate aminotransferase increased (Gr 2)
	Weight loss		Weight loss (Gr 2)
METABOLISM AND NUTRITION DISORDERS			
Anorexia			Anorexia (Gr 2)
Hyperphosphatemia			Hyperphosphatemia (Gr 2)
MUSCULOSKELETAL AND CONNECTIVE TISSUE DISORDERS			
	Arthralgia		Arthralgia (Gr 2)
	Back pain		Back pain (Gr 2)
NERVOUS SYSTEM DISORDERS			
	Dysgeusia		Dysgeusia (Gr 2)
RESPIRATORY, THORACIC AND MEDIASTINAL DISORDERS			
	Cough		Cough (Gr 2)
	Dyspnea		Dyspnea (Gr 2)
	Epistaxis		Epistaxis (Gr 2)
	Respiratory, thoracic and mediastinal disorders - Other (nasal dryness)		
SKIN AND SUBCUTANEOUS TISSUE DISORDERS			
	Alopecia		Alopecia (Gr 2)
Dry skin			Dry skin (Gr 2)
	Palmar-plantar erythrodysesthesia syndrome		Palmar-plantar erythrodysesthesia syndrome (Gr 2)
	Pruritus		
Skin and subcutaneous tissue disorders - Other (nail disorder) ⁴			Skin and subcutaneous tissue disorders - Other (nail disorder)⁴ (Gr 2)
	Skin and subcutaneous tissue disorders - Other (skin fissures)		

¹This table will be updated as the toxicity profile of the agent is revised. Updates will be distributed to all Principal Investigators at the time of revision. The current version can be obtained by contacting [contact]. Your name, the name of the investigator, the protocol and the agent should be included in the e-mail.

²Central serous retinopathy includes: chorioretinopathy, retinal detachment, retinal oedema, detachment of retinal pigment epithelium, detachment of macular retinal pigment epithelium, retinopathy and vitreous detachment.

³Eye disorders includes, but is not limited to eye disorder with redness and irritation of the eye, maybe associated with increased tearing of the eyes, itchy eyes, and inflamed eyes.

⁴Nail disorder includes, but is not limited to, onycholysis, onychalgia, onychoclasia, nail dystrophy, nail loss, nail bed bleeding, nail bed inflammation, nail discomfort, nail discoloration, and nail ridging.

Adverse events reported on Erdafitinib (JNJ-42756493) trials, but for which there is insufficient evidence to suggest that there was a reasonable possibility that Erdafitinib (JNJ-42756493) caused the adverse event:

BLOOD AND LYMPHATIC SYSTEM DISORDERS - Blood and lymphatic system disorders - Other (lymphadenopathy)

CARDIAC DISORDERS - Sinus tachycardia

EYE DISORDERS - Blurred vision; Eye disorders - Other (blepharitis); Eye disorders - Other (blindness unilateral); Eye disorders - Other (corneal erosion); Eye disorders - Other (corneal infiltrates); Eye disorders - Other (eyelid edema); Eye disorders - Other (foreign body sensation in eyes); Eye disorders - Other (lagophthalmos); Eye disorders - Other (macular degeneration); Eye disorders - Other (metamorphopsia); Eye disorders - Other (ocular hyperemia); Eye disorders - Other (xanthopsia); Eye pain; Night blindness; Papilledema; Photophobia; Vision decreased

GASTROINTESTINAL DISORDERS - Abdominal distension; Ascites; Colitis; Dysphagia; Gastrointestinal disorders - Other (intestinal obstruction); Salivary duct inflammation

GENERAL DISORDERS AND ADMINISTRATION SITE CONDITIONS - Edema limbs; General disorders and administration site conditions - Other (general physical health deterioration); Non-cardiac chest pain; Pain

INFECTIONS AND INFESTATIONS - Herpes simplex reactivation; Infections and infestations - Other (clostridium difficile colitis); Infections and infestations - Other (lower respiratory tract infection); Infections and infestations - Other (oral herpes); Sepsis; Urinary tract infection

INVESTIGATIONS - Alkaline phosphatase increased; Creatinine increased; GGT increased

METABOLISM AND NUTRITION DISORDERS - Dehydration; Hypercalcemia; Hypoalbuminemia; Hypocalcemia; Hyponatremia; Hypophosphatemia

NEOPLASMS BENIGN, MALIGNANT AND UNSPECIFIED (INCL CYSTS AND POLYPS) - Neoplasms benign, malignant and unspecified (incl cysts and polyps) - Other (metastases to spine)

NERVOUS SYSTEM DISORDERS - Lethargy; Somnolence

PSYCHIATRIC DISORDERS - Insomnia

RENAL AND URINARY DISORDERS - Acute kidney injury

RESPIRATORY, THORACIC AND MEDIASTINAL DISORDERS - Hypoxia; Pleural effusion; Respiratory, thoracic and mediastinal disorders - Other (respiratory distress)

SKIN AND SUBCUTANEOUS TISSUE DISORDERS - Bullous dermatitis; Eczema; Hyperkeratosis; Rash maculo-papular; Skin and subcutaneous tissue disorders - Other (cutaneous calcification); Skin and subcutaneous tissue disorders - Other (skin exfoliation); Skin and subcutaneous tissue disorders - Other (skin lesion); Skin and subcutaneous tissue disorders - Other (skin toxicity); Skin atrophy; Skin hyperpigmentation; Skin ulceration

VASCULAR DISORDERS - Hypotension; Thromboembolic event

NOTE: Erdafitinib (JNJ-42756493) in combination with other agents could cause an exacerbation of any adverse event currently known to be caused by the other agent, or the combination may result in events never previously associated with either agent.

